1. Asian (self-report and be confirmed by PI observation)
2. Ages between 18 and 39 years
3. Vertexed corrected sphere power between -0.50 and -6.00 D
4. Vertexed refractive cylinder power between -0.75 and -1.50 D
5. Best corrected acuity of 20/25 or better in each eye
6. Habitual soft contact lens wearers at least 6 months (who should be successfully fitted with both DT1 Spherical and Toric contact lens)

Exclusion Criteria:

1. History of ocular pathology or surgery
2. Active ocular infection or clinically significant ocular inflammation
3. Any significant binocular vision abnormalities
4. Wearers of gas-permeable lenses for at least 3 months prior to the study
5. Pregnant or lactating individuals (by self-report)

Study Design:

This study will follow a double-masked randomized crossover design^[10], where participants will be fitted with DAILIES TOTAL1® for Astigmatism and DAILIES TOTAL1® Spherical Contact Lenses in a randomized order. Each participant will use both types of lenses over different periods. The study will be composed of five visits:

	Visit 1 (Baseline and fitting for lens 1)	Visit 2 (D2±1 lens 1 follow-up)	Visit 3 (D4 ±1 Outcomes for lens 1 and fitting for lens 2)	Visit 4 (D6 ±1 lens 2 follow-up)	Visit 5 (D8 ±1 Outcomes for lens 2)
Inclusion/Exclusion Criteria Screening	X				
Fitting	X		X		
NAVQ test	X		X		X
high-contrast, high-luminance and low-contrast, high-luminance visual acuity at 40 cm and 6 m (logMAR) by EyeChart PRO and E-ETDRS (NIDEK SC-2000)			X		X
MNREAD reading performance test	X		X		X
Slit lamp assessment & over-refraction	X	X	X	X	X

The assessments will be conducted following the sequence in this table

Timeline:

Each lens pair will be measured three times: Fitting, follow-up and outcome measurement

Visit 1 - Baseline Evaluation and Fitting for Lens 1

1. Obtain informed consent.
2. Collect subject demographics, medical and ocular health, and information on concomitant medications.
3. Measure binocular near logMAR visual acuity with the participant's habitual correction.
4. Administer the Near Activity Visual Questionnaire (NAVQ) to gauge the participant's subjective experience of near vision function. ^[11]
5. Evaluate the participant's reading performance, speed, and functionality with the MNREAD app. This will involve:

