 - i. Reading Acuity: Determine the smallest print size so that the participant can accurately read without making significant errors. The app will present sentences in various print sizes, starting from larger to smaller.
 - ii. Critical Print Size: Identify the smallest print size that the participant can read at their fastest speed. This will be determined by observing the smallest print size read at the maximum speed by the participant.
 - iii. Maximum Reading Speed: Assess by presenting sentences in a print size comfortable for the participant, then timing how long it takes for them to read these sentences. The reading speed will be computed in words per minute.
 - iv. Reading Accessibility Index: Calculate this single-value measure, which represents a person's visual access to commonly encountered printed material, using data from the previous steps.
6. Conduct manifest refraction using maximum plus to best visual acuity.
7. Assess accommodation and binocular vision.
8. Measure pupil size in dim and bright light settings.
9. Complete an anterior segment slit lamp examination.
10. After confirming eligibility, randomize and fit the subject with the first pair of contact lenses.
11. Allow the contact lenses to settle for 10 minutes before evaluating the fit.
12. Perform an over-refraction and adjust the lens power if necessary.

Visit 2 - Contact Lens Follow-up 1

1. Assess the subject who should be wearing the assigned study contact lenses for at least 2 hours before the appointment.
2. Perform an over-refraction and adjust the lens power if necessary.
3. Conduct a slit lamp examination including ocular surface evaluation with sodium fluorescein after the contact lenses are removed.

Visit 3 - Outcome Measures for Lens 1 and Fitting for Lens 2

1. Have the subject report to the visit wearing their assigned study contact lenses for at least 2 hours before their appointment.
2. Administer the NAVQ.
3. Conduct high-contrast, high-luminance visual acuity at 40 cm & 6 m and low-contrast, high-luminance visual acuity at 6m
4. Evaluate the participant's reading performance, speed, and functionality with the MNREAD app

5. Perform a slit lamp examination including sodium fluorescein after removing the study contact lenses.
6. Fit the subject with the second pair of contact lenses based on the randomization schedule.
7. Allow the contact lenses to settle for 10 minutes before evaluating.

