8. Perform an overrefraction and adjust the power of the alternate lenses if necessary.

Visits 4 and 5 - Contact Lens Follow-up 2 and Outcome Measures for Lens 2

1. Repeat the procedures from Visits 2 and 3 respectively for the second pair of lenses.

Randomization:

- Create a computer-generated list with 39 elements, each representing a type of lens (label "A" for DAILIES TOTAL1® for Astigmatism and "B" for DAILIES TOTAL1® Spherical Contact Lenses).
- Shuffle the elements of the list to ensure random assignment.
- Attach a coded sticker to each lens' blister packaging, corresponding to the codes in the computer-generated list.

Note: Only a designated unmasked examiner, who does not interact directly with the participants or influence the data collection, interpretation, or analysis, will have access to the decoding key for these stickers.

Visit 1:

- After confirming eligibility, the unmasked examiner consults the randomization list and selects the appropriately coded package for the participant.
- The unmasked examiner hands off the coded package to the masked examiner.
- The masked examiner fits the subject with the first pair of lenses, without knowing the type of lens they are administering.

Visit 3:

- Repeat the process from Visit 1: the unmasked examiner, based on the randomization list, selects the second pair of lenses for the participant.
- The unmasked examiner hands off the coded package to the masked examiner.
- The masked examiner fits the subject with the second pair of lenses, maintaining the blindness of the study.

End of Study:

- At the end of the study, the unmasked examiner references the coding key to reveal the order in which the lenses were administered to each participant, allowing the research team to analyze the results accordingly.
- This point form process ensures a robust double-blind crossover design, where the participants and the majority of the research team are not aware of the lens type being used at any point, reducing potential biases.

Endpoints:

Primary Endpoints:

1. Evaluate near (40cm) high-contrast visual acuity in logMAR by i-Pad-based applications – EyeChart PRO

Secondary Endpoints:

1. Evaluate participant's reading acuity, critical print size, maximum reading speed, and reading accessibility index using the MNREAD app. Specifically:

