 - i. Reading Acuity: Identify the smallest print size that can be accurately read by the participant without significant errors. This is done by presenting sentences in decreasing print sizes.
 - ii. Critical Print Size: Determine the smallest print size that the participant can read at their fastest reading speed.
 - iii. Maximum Reading Speed: Measure by timing how long the participant takes to read sentences presented in a comfortable print size. The speed is calculated as words per minute.
 - iv. Reading Accessibility Index: Compute this single-value metric, indicative of a person's visual access to commonly encountered printed text, using data from the previous steps.
2. Evaluate the near visual function with the Near Activity Visual Questionnaire
3. Distance high-low contrast visual acuity in logMAR by using E-ETDRS (NIDEK SC-2000)

Sample size justification

1. The sample size for this study was calculated based on the results of a similar study [12] that assessed improvements in near high- and low-contrast visual acuity among astigmatic patients using toric contact lenses versus spherical contact lenses.
2. The primary endpoint for our study is like the referenced study, and we expect a 1-line treatment benefit (0.1 logMAR) as the minimum clinically important difference. The within-subject standard deviation of the outcome measure is also anticipated to be a line (0.1 logMAR) based on the referenced study.
3. To ensure adequate power for our study, set the significance level (α) at 0.05 (2-sided) and the power ($1-\beta$) at 0.80. Using these parameters and the formula for sample size calculation in a crossover design, we estimated a sample size of 35 participants.
4. A dropout rate of approximately 10%. To ensure sufficient power to detect a statistically and clinically significant difference in our primary outcome, we plan to enrol 39 participants in this clinical trial.

Statistical Analysis:

The treatment effects will be analyzed using the Grizzle model for the two-period, two-treatment crossover trial^[10]. The data will first be tested for the presence of a carryover effect according to the sequence of randomization, that is, sphere or toric, during the first period at the critical level of 0.10. Then, the treatment effect will be estimated using a linear mixed model in the presence of period and sequence effects to obtain unbiased effect sizes^[10].

Reference:

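### Is the primary acuity endpoint left undefined because the plan does not say which eye or eyes are tested?

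*Combined protocol and SAP*

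**What the plan says.** The combined protocol and SAP describes the outcome acuity in these places:

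- Study Design, schedule table, marked at Visits 3 and 5 only: "high-contrast, high-luminance and low-contrast, high-luminance visual acuity at 40 cm and 6 m (logMAR", followed by the names of both instruments, EyeChart PRO and E-ETDRS (NIDEK SC-2000).
- Visit 3, step 3: "Conduct high-contrast, high-luminance visual acuity at 40 cm & 6 m and low-contrast, high-luminance visual acuity at 6m". Visit 5 inherits this: "Repeat the procedures from Visits 2 and 3 respectively for the second pair of lenses".
- Primary Endpoints, item 1: "Evaluate near (40cm) high-contrast visual acuity in logMAR by i-Pad-based applications", with EyeChart PRO as the application.
- Secondary Endpoints, item 3: "Distance high-low contrast visual acuity in logMAR by using E-ETDRS", on the NIDEK SC-2000.

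None of these names the eye or eyes. Two other acuity statements do. Visit 1, step 3 reads "Measure binocular near logMAR visual acuity with the participant's habitual correction", and Inclusion Criteria, item 5 reads "Best corrected acuity of 20/25 or better in each eye".

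The Sample size justification (item 2) says "The within-subject standard deviation of the outcome measure is also anticipated to be a line (0.1 logMAR" and goes on to count participants: 35 evaluable, 39 enrolled. The Statistical Analysis section plans a Grizzle two-period crossover analysis and a linear mixed model with period and sequence effects. It mentions no eye term.

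**The concern.** Which eye is tested settles both what the primary endpoint measures and how many values each participant contributes. Binocular testing gives one value per lens. Testing each eye gives two correlated values, and the plan does not say whether to use one eye, the mean, or both. If both were entered as independent, the standard error of the toric-minus-sphere difference would be too small and the test would reject too often. The anticipated SD of 0.1 logMAR would also be tied to a measure that is not named. Because the lens key is opened at the end of the study, a rule for combining eyes could be chosen with lens identity known.

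A smaller worry is the schedule table. It lists two contrasts, two distances and two instruments without pairing them, so it can be read as including low contrast at 40 cm, which Visit 3, step 3 does not.

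**Working it through.** **The stated sample size.** Inputs from the Sample size justification: difference 0.1 logMAR, within-subject SD 0.1 logMAR, two-sided alpha 0.05, power 0.80.

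- Crossover formula: N = 2 × (1.960 + 0.842)² × 0.1² / 0.1² = 15.7, so 16 in total. A t-based version gives 18.
- The stated 35 is therefore not reproduced by the crossover formula. That is a separate matter and does not turn on which eye is tested.
- Enrolment does reproduce: 35 / (1 − 0.10) = 38.9, so 39.
- With these inputs, power at 35 is about 98%.

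**Number of primary readings over Visits 3 and 5.** Binocular: 1 × 2 = 2 per participant, or 70 for 35 and 78 for 39. Per eye: 2 × 2 = 4 per participant, or 140 and 156.

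**If eyes are tested separately and averaged.** Assume that 0.1 is the within-subject SD for one eye, and let r be the between-eye correlation of the lens difference. The documents give no r, so the full range 0 to 1 is shown. The SD of the averaged difference is 0.1 × √2 × √((1 + r)/2) = 0.1 × √(1 + r).

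| r | SD of difference | N for 80% power | Power at 35 |
|---|---|---|---|
| 0 | 0.100 | 11 | above 99.9% |
| 0.5 | 0.122 | 14 | 99.7% |
| 1 | 0.141 | 18 | 98.2% |

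A single pre-chosen eye has the same SD as the last row (0.1 × √2 = 0.141).

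**If both eyes are entered as independent.** The true standard error is √(1 + r) times the reported one, and the false-positive rate of a nominal 5% test is 2 × (1 − Φ(1.96/√(1 + r))).

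| r (assumed) | True / reported SE | False-positive rate |
|---|---|---|
| 0.3 | 1.14 | 8.6% |
| 0.5 | 1.22 | about 11% |
| 0.8 | 1.34 | 14.4% |

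A simulation with 35 participants (18 and 17 per sequence, 40,000 runs) gives 8.6%, 11.0% and 14.8%.

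**Which reading the plan supports.**

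- The only near acuity step that names the eyes is binocular. The per-eye wording belongs to an eligibility rule on best corrected acuity.
- Lenses are fitted as a pair of one type in each period, and the randomization list has 39 elements for 39 participants. The participant is the randomised unit.
- The sample size is in participants and uses a within-subject SD.
- In its basic form the two-period crossover model takes one response per participant per period.

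**Contrast, distance and instrument.** The primary endpoint line puts 40 cm, high contrast and EyeChart PRO together. Secondary endpoint 3 puts distance, both contrasts and E-ETDRS together. Visit 3, step 3 gives the same three conditions and adds luminance. Crossing everything in the table gives 2 × 2 × 2 = 8 combinations against those 3, but that counts crossings and not competing instructions, since several pair an instrument with the other one's distance.

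**The case for a change.** The strongest case for a change is that likely intent is not a specification. Examiners work from step 3 as written, the primary endpoint of a randomised trial should be reproducible from its text, and the repair would be a single word. If per-eye data were collected, the mixed model as described would not protect the test. A participant random intercept alone does not carry the correlation between the two eyes' lens differences, and the choice among right eye, mean or both could be made after the key is opened.

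Part of this stands. No passage attaches an eye to the outcome reading, and the unnamed rule for combining eyes would matter if testing were per eye. But whether eyes are tested together or separately is settled at data collection, by an examiner who does not know the lens. If readings are binocular, nothing remains to be chosen later. If they are per eye, a mean or one fixed eye gives a valid participant-level analysis with ample power. Only treating eyes as independent does damage, and nothing in the plan suggests that.

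**Conclusion.** No change to the plan is needed. The eye tested is a missing detail that a competent team would fill by carrying the binocular reading of Visit 1 into Visits 3 and 5, giving one value per participant per lens. On that reading error rates are unaffected. If the two eyes were averaged, power at 35 would still be at least about 98%, assuming the plan's 0.1 logMAR applies to one eye. The 8.6% to 14% false-positive range is arithmetically right, but it rests on per-eye testing, both eyes analysed as independent, and an assumed correlation of 0.3 to 0.8. The plan states none of these, so the range does not measure a fault in it. The schedule table is compressed wording that the step and the endpoint list already resolve; aligning it would change no endpoint, sample size or conclusion. The conclusion would weaken only if eyes were in fact tested separately and no single participant-level value were fixed before unmasking.

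### The stated sample size of 35 does not follow from the stated inputs: the crossover formula gives 16 to 18 for 80% power, and 35 gives about 98%

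*Combined protocol and SAP*

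**What the plan says.** All the inputs stand in the combined protocol and SAP, under Sample size justification.

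- Item 1 gives the source: "The sample size for this study was calculated based on the results of a similar study". That study is described as covering near acuity at both high and low contrast.
- Item 2 gives the difference: "we expect a 1-line treatment benefit (0.1 logMAR) as the minimum clinically important difference".
- Item 2 gives the variability: "The within-subject standard deviation of the outcome measure is also anticipated to be a line (0.1 logMAR) based on the referenced study".
- Item 3 sets two-sided alpha at 0.05 and power at 0.80, then states the result: "Using these parameters and the formula for sample size calculation in a crossover design, we estimated a sample size of 35 participants".
- Item 4 allows for about 10% dropout: "we plan to enrol 39 participants in this clinical trial".

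The Study Design section has every participant wear both lens types. The Statistical Analysis section names a model for the two-period, two-treatment crossover. The design, the analysis and the named formula therefore agree on a within-subject comparison. The primary endpoint is near high-contrast acuity at 40 cm.

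**The concern.** Difference, SD, alpha, power and design are all stated, and 35 is presented as what the formula returns. It is not presented as a rounded-up figure or one with a margin for secondary endpoints. The result can therefore be checked, and it is about twice what the inputs require.

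The consequence depends on which element is wrong. If the SD of 0.10 is right, the trial has far more power than the 80% it claims. If 35 really was the 80% figure, a larger SD was used, the written SD is wrong, and the trial has little to spare. The plan does not let the reader distinguish these cases. It also does not say whether 0.1 was taken from the high-contrast or the low-contrast results of the referenced study.

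**Working it through.** **Inputs** (Sample size justification, items 2 to 4): difference δ = 0.1; within-subject SD σ = 0.1; two-sided α = 0.05; power 0.80; stated N = 35 evaluable, 39 enrolled.

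**Step 1. Crossover formula, normal approximation.** The treatment difference has variance 2σ²/N, so

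N = 2 (z₀.₉₇₅ + z₀.₈₀)² σ²/δ² = 2 × (1.960 + 0.842)² × 0.1²/0.1² = 2 × 7.849 = 15.7, so 16.

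The plan's 35 is not reproduced.

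**Step 2. The same with the noncentral t distribution.** SE = σ √[(1/n₁ + 1/n₂)/2], with n₁ and n₂ the two sequence groups and N − 2 degrees of freedom.

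| N | Power |
|---|---|
| 16 | 74.9% |
| 17 | 77.6% |
| 18 | 80.4% |
| 35 | 98.2% |
| 39 | 99.0% |

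The smallest N for 80% power is 18. With 35 evaluable and σ = 0.10, the difference detectable at 80% power is 0.069 logMAR.

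**Step 3. Other readings of the inputs.**

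| Reading | N required |
|---|---|
| 0.1 is the SD of the paired difference | 8 (normal), 10 to 11 (t) |
| One-sided α 0.05 | 13 (normal) |
| Two-sided α 0.025 | 20 (normal) |
| Power 90% | 22 (normal), 24 (t) |
| Power 95% | 26 (normal), 29 (t) |
| Parallel-group formula, SD 0.1, total N | 32 (normal), 34 (t, 80.7%) |
| Paired analysis, SD of difference 0.2 | 32 (normal), 34 (t, 80.8%) |

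Only the last two come near 35, and neither returns it. The parallel-group formula is not the crossover formula that item 3 names. An SD of difference of 0.2 does not match a within-subject SD of 0.1, which implies √2 × 0.1 = 0.141.

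**Step 4. The SD that would make 35 correct.** Solving Step 2 for 80% power gives σ = 0.1449 at N = 35 and 0.1534 at N = 39. The normal approximation at N = 35 gives 0.1 × √(35/2)/2.802 = 0.149.

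**Step 5. Power over an assumed range of SD.** The documents give only 0.10; the other values are assumptions.

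| Within-subject SD | Power at 35 | Power at 39 |
|---|---|---|
| 0.10 | 98.2% | 99.0% |
| 0.11 | 95.8% | 97.4% |
| 0.12 | 92.2% | 94.8% |
| 0.13 | 87.7% | 91.1% |
| 0.145 | 79.9% | 84.2% |
| 0.15 | 77.2% | 81.7% |

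**Step 6. Dropout.** 35/0.9 = 38.9, so 39. This step reproduces and cannot be where the discrepancy arises.

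**The case against.** The best case for the plan is that the slip may lie in the formula alone. A parallel-group t calculation with the SD exactly as written gives 34 in total, one short of 35. If that is what happened, the SD of 0.1 is sound and N is merely generous. On this view the value 0.145 is only a back-calculation that appears nowhere in the documents, and it should not be adopted to rescue N. Enrolling more than the minimum is also no defect in itself. Even with an SD half as large again (0.15), power would be 77% at 35 and 82% at 39.

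Much of this stands. A formula slip is plausible, the error is conservative on the stated inputs, and 0.145 must not be written in unless it was the value used. It does not rescue the statement. The parallel-group route contradicts the crossover formula that the plan names and still does not give 35. If it was used, N is the wrong element and the claimed 80% still misdescribes the trial. The plan offers no margin or secondary endpoint as a reason for going above the calculated number.

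Item 2 does call 0.1 a within-subject SD, so the paired-difference reading is the less natural one. It also moves the answer further from 35.

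**Conclusion.** The point holds. On the stated inputs the crossover needs 16 participants (normal approximation) or 18 (t-based) for 80% power, and the stated 35 gives about 98%. No reading consistent with the named design and the written SD gives 35. The documents do not show whether N, the SD or the power is misstated, and the SD in the referenced study cannot be checked from them.

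The calculation assumes the standard two-period, two-treatment crossover, σ as the within-subject SD, near-equal sequence groups and no carryover.

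This is a correction of a stated figure and should be made. It does not threaten the result: with SD 0.10 the trial exceeds its power target, and type I error and the treatment estimate are untouched. Only a true within-subject SD above about 0.145 would leave 35 evaluable participants below 80%.

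**What to change.** Keep enrolment at 39. In Sample size justification:

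1. Write out the formula used.
2. State whether 0.1 is the within-subject SD or the SD of the paired difference, which is 1.41 times the within-subject SD.
3. Check the value against the referenced study for near high-contrast acuity, the primary endpoint.
4. Restate N, SD and power so that they agree.

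If SD 0.10 is confirmed, suitable wording is:

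> Thirty-five evaluable participants (39 enrolled) give about 98% power to detect 0.10 logMAR, or 80% power to detect about 0.07 logMAR, with within-subject SD 0.10 and two-sided alpha 0.05.

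Only if the sponsor's records show that an SD of about 0.145 was used:

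> With within-subject SD 0.145 logMAR, 35 evaluable participants (39 enrolled) give 80% power to detect 0.10 logMAR at two-sided alpha 0.05.

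For any other SD, state that SD and its power; at 35 evaluable, for example, 0.12 gives 92% and 0.13 gives 88%. The SD should come from the source, not be chosen to fit N.

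The cost is a few lines of protocol text and one look at the referenced study, with no change to enrolment.

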Proposal Title:

A Comparative Study on Functional Vision and Digital Device Usage in Astigmatic Patients: DAILIES TOTAL1 Toric Contact Lenses vs. Spherical Equivalent Contact Lenses in Asian Eyes

[name], Principal Researcher, Mopsy Research

DATE: 20 DEC 2023

Background:

In today's digital age, individuals spend a significant amount of time using digital devices ^[1]. This is notably challenging for individuals with astigmatism, a condition that can impair visual acuity when using these devices ^[2]. Despite the prevalence of astigmatism, toric contact lens technology, which can potentially improve visual acuity for these individuals, remains underused ^{[3][4]}. Many eye care practitioners opt for spherical lenses due to perceived complexities of fitting and considerations of cost-effectiveness ^{[5][6]}.

DAILIES TOTAL1[®] for Astigmatism contact lenses, the first and only daily disposable Water Gradient toric contact lenses, can potentially address this issue. These lenses represent a significant innovation in toric contact lens technology, offering a unique combination of breathability and exceptional comfort. The lenses utilize Water Gradient Technology, creating a gradual transition in water content from the core to the surface of the lens, with the water content approaching 100% at the lens surface. This technology enables these lenses to offer a combination of high breathability and exceptional comfort.

Unmet Medical Need:

Although toric lenses, including DAILIES TOTAL1[®] for Astigmatism, have been shown to improve visual acuity in astigmatic patients, their impact on real-world visual performance, particularly when using digital devices, is less understood ^[1]. Additionally, while many practitioners gravitate towards spherical lenses, astigmatic patients could greatly benefit from the comfort and visual acuity provided by DAILIES TOTAL1[®] for Astigmatism contact lenses.

Gaining insights into the real-world visual performance of astigmatic patients when using DAILIES TOTAL1[®] for Astigmatism contact lenses could provide valuable information to eye care practitioners and patients. This could potentially encourage the broader adoption of DAILIES TOTAL1[®] for Astigmatism contact lenses, improving the visual experience for astigmatic patients and addressing an unmet medical need.

Scientific Rationale:

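### Does the carryover test at 0.10, with no stated consequence, undermine the lens comparison or its claim to be unbiased?

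*Combined protocol and SAP*

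**What the plan says.** The whole analysis plan is the short Statistical Analysis section of the combined protocol and SAP. It names the Grizzle model for a two-period, two-treatment crossover and describes two steps.

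- Step one: "The data will first be tested for the presence of a carryover effect according to the sequence of randomization". The sequence is explained as sphere or toric "during the first period at the critical level of 0.10".
- Step two: "Then, the treatment effect will be estimated using a linear mixed model", "in the presence of period and sequence effects to obtain unbiased effect sizes".

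No sentence links the result of step one to what is done in step two, and none states an assumption about carryover.

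Other sections bear on the point:

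- Randomization, End of Study: before the analysis, "the unmasked examiner references the coding key to reveal the order in which the lenses were administered to each participant".
- Background: the toric lens is described as "the first and only daily disposable Water Gradient toric contact lenses". The spherical lens is not described in those terms.
- Visit 3, repeated at Visit 5: participants attend "wearing their assigned study contact lenses for at least 2 hours before their appointment".
- Study Design, visit table: lens 2 is fitted at Visit 3 (day 4 ±1), the visit at which lens 1 outcomes are taken. Its own outcomes come at "Visit 5 (D8 ±1 Outcomes for lens 2".

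**The concern.** There are two separate worries.

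First, a test carried out before the main analysis, at its own level of 0.10, leads the reader to expect a decision, and none is written. With no carryover at all the test is significant in about 10% of trials, so the team could well face the question, and would face it with lens order known. If they responded by analysing the first period only, the stated 5% error would no longer hold and power would fall.

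Second, the word unbiased is stronger than the model can deliver unaided. In a two-period, two-lens crossover, unequal carryover cannot be separated from a difference between sequences, so a sequence term does not take it out of the lens effect. The estimate is unbiased only if the two lenses carry over equally. The plan does not say so, and it has no washout between lenses. Passing the carryover test is no substitute, because the test is weak at this sample size.

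At stake would be the error rate and the bias of the primary comparison, near high-contrast acuity.

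**Working it through.** **Inputs from the plan (Sample size justification).** Within-subject SD 0.1 logMAR, target difference 0.1 logMAR, two-sided 5% level, 35 evaluable participants, 39 enrolled. The dropout step reproduces: 35/0.9 = 38.9, so 39. The 35 does not follow from the usual crossover formula: 2 × (1.960 + 0.842)² × (0.1/0.1)² = 15.7, so 16, or 18 with the t distribution. That is a separate matter, and 35 is taken here as given.

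**Assumptions.** A split of 17 and 18 between sequences. Between-person SD 0.05 to 0.15 logMAR, which the documents do not give. The SD of 0.1 is read as applying to each measurement. The carryover test is a t test on each person's total over both periods, since the plan does not specify its form.

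**What the model estimates.** Let τ be the lens effect (toric minus sphere) and λ the carryover difference (toric minus sphere). The expected value of period 1 minus period 2 is:

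- toric first: (period effect) + τ − λ
- sphere first: (period effect) − τ

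Half the difference between the sequences is τ − λ/2. The difference between sequences in mean total is λ. So the carryover test examines λ, and the lens estimate is off by λ/2 whether or not a sequence term is fitted.

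**Precision.** √(1/17 + 1/18) = 0.338. The SD of a within-person difference is √2 × 0.1 = 0.141. The standard error of the lens effect is 0.5 × 0.141 × 0.338 = 0.0239. The ratio 0.10/0.0239 is 4.18, which gives 98% power on 33 degrees of freedom.

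**Plan followed as written (mixed model every time).** With no carryover, simulated type I error is 4.9% to 5.1% over the range of between-person SD. The carryover test is significant in about 10% of trials and alters nothing.

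**A switch the plan does not contain.** If a significant test sent the analysis to first-period data, with 100,000 to 200,000 simulated trials per setting:

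| Between-person SD | Type I error | Power at 0.10 logMAR |
|---|---|---|
| 0.05 | 7.3–7.5% | 94% |
| 0.10 | 8.1–8.3% | 93% |
| 0.15 | 8.7–8.8% | 93–94% |

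**Bias from unequal carryover.** The sizes are illustrative, because the documents give none.

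| λ (logMAR) | Bias λ/2 | Bias / 0.0239 | 95% interval coverage | Carryover test significant |
|---|---|---|---|---|
| 0.01 | 0.005 | 0.21 | 94.5% | not run |
| 0.02 | 0.010 | 0.42 | 93.1% | 10–12% |
| 0.05 | 0.025 | 1.05 | 82.6% | 13–22% |

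The mean bias is the same in trials that pass the carryover test. The 95% interval for λ has half-width 2.03 × √(2 × 0.1² + 4 × SD²) × 0.338, where SD is the between-person SD: 0.12, 0.17 and 0.23 logMAR for 0.05, 0.10 and 0.15. The test therefore says little about carryover of a plausible size.

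**How long lens 2 is worn before its outcomes.** Nominally 8 − 4 = 4 days. With the visit windows, the shortest interval is 7 − 5 = 2 days and the longest 9 − 3 = 6 days.

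**Which data are tested.** The phrase about the first period follows the explanation of sequence as sphere or toric. It reads most naturally as naming the two sequence groups by the lens worn first. It does not restrict the test to first-period data.

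**The case for a change.** The strongest case for a change starts from the analysis coming after lens order is revealed. A test with its own threshold and no consequence then leaves a choice open at the worst moment. The citation of a named crossover model might be taken to bring a two-stage rule with it. The bias argument needs no guess about the team's behaviour, since it follows from the design. The remedy would cost only a sentence or two.

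Much of this stands as description. The plan should not be read as having shown that carryover is absent, a non-significant test would not show it, and unbiased is conditional on equal carryover.

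It does not stand as a reason to change the plan. The step to the mixed model has no condition attached, so a switch to first-period data would depart from the written plan. The cited source is not available here and cannot be used to read a switch into the text. The bias is only as large as the carryover, and no mechanism is offered for a lens no longer worn to alter acuity measured through a different lens days later. Coverage of 83% needs a carryover difference of 0.05 logMAR, half of what the plan treats as the minimum important difference. If part of the toric lens's benefit did persist into the second period, λ would have the sign of τ and the estimate would shrink toward zero, against the trial's hypothesis. Persistence is harder to rule out for the questionnaire and reading measures, but those are secondary.

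**Conclusion.** No change follows. The carryover test is idle. Followed as written, the plan fits one mixed model whatever the test shows, with type I error of 5% and, at the stated SD with 35 evaluable participants, 98% power for 0.10 logMAR. The 7% to 9% error and the fall in power to 93–94% belong to a procedure the plan does not specify.

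The unstated assumption of equal carryover is the usual one for this design, and an analyst would report the lens effect on that footing. Its cost is half of any carryover difference: 0.005 logMAR at 0.01 and 0.010 at 0.02, with coverage of 94.5% and 93.1%. Measurement in the assigned lens after at least 2 hours of wear, and 2 to 6 days after lens 2 is fitted, makes a large difference in acuity carryover unlikely, although the documents contain no data on it.

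Writing these points out would add clarity, but the model, the estimate, the test and the conclusion would stay as they are. The figures rest on the 17 and 18 split, the assumed between-person SD of 0.05 to 0.15, and the stated SD of 0.1 applying to each measurement. The main conclusion rests only on the unconditional wording of the second step.
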